in the current FDA-approved product labeling for that device (i.e., for an “off-label” indication)?

* No

- 2.2.2.1.1 List each of the devices being evaluated for an “off-label” indication. Specify for each listed device the corresponding Investigational Device Exemption (IDE) number for this device/research study; or provide a justification for why you feel that this device and its “off-label” use, as proposed in this research study (i.e., to include potential failure of the device) constitute a non-significant risk to the involved research subjects.

*

| Device | IDE # | Non-significant risk justification |
|--------|-------|------------------------------------|
|--------|-------|------------------------------------|

There are no items to display

[reviewer notes-]

Section 2 - Research Design and Methods

- 2.3 Summarize the general classification (e.g., descriptive, experimental) and methodological design (e.g., observational, cross-sectional, longitudinal, randomized, open-label single-blind, double-blind, placebo-controlled, active treatment controlled, parallel arm, cross-over arm) of the proposed research study, as applicable.

Prospective, Randomized, Non-blinded, Surgical outcomes, Pilot study assessing clinical outcomes following fat grafting for pain at amputation sites (with and without adipose stem cell enrichment).

- 2.3.1 Does this research study involve a placebo-controlled arm?

* No

[reviewer notes-]

Section 2 - Research Design and Methods

- 2.4 Will any research subjects be withdrawn from known effective therapy for the purpose of participating in this research study?

Section: Section 2 - Research Design and Methods

* No

- 2.4.1 Provide a justification for discontinuing subjects from known effective therapy for the purpose of study participation.
- 2.4.2 Describe the risks to subjects associated with discontinuing them from known effective therapy for the purpose of study participation.

[reviewer notes-]

Section 2 - Research Design and Methods

- 2.5 Will screening procedures (i.e., procedures to determine research subject eligibility) be performed specifically for the purpose of this research study?

* Yes

- 2.5.1 List the screening procedures that will be performed for the purpose of this research study. Do NOT include the inclusion/exclusion criteria in this section as they will be addressed in section 3; questions 3.13 and 3.14.

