
recordings. 3.) All participants who are women of child bearing potential will receive a urine pregnancy dip test. If the test result is positive the subject will not continue participation in this research study. 4.) Collection and review of new medications to include prescription and vitamins / supplements, allergies and vital signs (Temp, HR, Resp, BP), weight, body mass index (BMI) calculation, and adverse event reporting. 5.) Serial Computed Tomography Imaging or MRI scan will be performed. A high resolution Computed Tomography (CT) Scan of the amputation stump will be performed at Presbyterian Hospital and will take approximately 60 minutes. This scan will be pre-procedural and will serve as a baseline. All CT scans will be performed on a 64-slice scanner (LightSpeed, GE Healthcare), using slice thickness of 1.25 mm and pitch of 1.375. kVp, mA, and FOV will be optimized to the subject and body part to be imaged. Soft tissue and bone kernels will be employed. These images will be volumetrically reformatted into coronal and sagittal planes for confirmation of findings. Additionally, surface-rendered volumetric reformats will be created emphasizing both bony structures and soft tissues. In the event that a CT scan is contraindicated or declined by a study participant, MRI will be performed using a 1.5 T MRI scanner (Signa HDx, GE Healthcare). The MR imaging protocols will include coronal and axial planes using T1-weighted spin echo sequences as well as coronal, axial, and sagittal planes using T2-weighted fast spin echo with fat suppression and/or short tau inversion recovery (STIR) sequences. Again, FOV, TR/TE time, acquisition time and other parameters will be optimized to the subject and body part to be imaged. Intravenous contrast will not be administered for either CT or MR imaging. Images will be reviewed by radiology. Volume measurements of the implanted material will be made on all post-procedural CTs or MRIs. These volumetric measurements are expected to be precise to within 5% of the actual volume of material. Trends in volume of tissue will be analyzed over time across the multiple CT or MRI scans. Both linear and volumetric measurements will be used to quantify implanted material. Subjects must remove compression sleeves prior to CT scans. 6.) To further evaluate pre-surgical amputation stump pain, the study coordinator will provide a Pain Assessment form to the participant to complete. This form will document the nature/charter of the discomfort limiting function and or interferes with their ability to use a prosthetic device. The subject will be instructed to document the discomfort to include frequency, location, intensity (1 to 10 scale with 10 as most intense), type of pain (physiological or phantom). It will include self interventions related to pain and use of prosthetic devices. 7.) Psychosocial Assessment: One of the aims of the proposed study is to evaluate pre- and post-operative quality of life and symptoms of psychological distress. This aim will also consider psychosocial factors (pre- and post- surgery) that predict psychological well-being and quality of life outcomes following surgery. The aim is important for identification of psychosocial factors that may play a role in and be critical to enhancing quality of life outcomes from amputation stump surgery. Participants will be asked to complete a psychosocial battery that includes: a) self-report measures of satisfaction with physical appearance, anxiety and depressive symptoms, social functioning and social avoidance and distress and; b) questionnaires that assess significant predictors of quality of life

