Visit 2 and/or 3 PO only the subject will be evaluated by the Prosthetic /Orthotics/Occupational therapy team (limited physical exam) in conjunction with the PI to determine weight bearing readiness as well as readiness to obtain a standard of care check socket by their primary prosthetist. The participant's prosthetic device (including check socket and or permanent socket) and any other assistive devices used will be fitted as part of their routine standard of care and will only be documented that the visit happened. The subject will be instructed NOT to wear the prosthetic sockets until seen by research team and/or clearance received to utilize any new prosthetic devices which is anticipated to occur at approximately POV3 or POV4. The subject may be asked to attend an interim visit at 4-5 months PO, if the check socket and permanent socket fabrication fall out of the PO visit 2-3 range. At Post op visit 4 (6 months post op), POV5 (month 12) and POV6 (month 24) the prosthetist and therapist will implement the assessments and select the appropriate assessments based on the participant's functional status, amputation site(s), and assistive technology used. The following assessments are dependent upon the location (upper verses lower extremity) and may or may not be completed depending upon the site of interest. a. Prosthetics Evaluation Questionnaire (PEQ) is a self-report questionnaire containing 54 questions organized into nine functional domains related to prosthesis-related changes in quality of life. The PEQ was developed to fill the need for a comprehensive self-report instrument for individuals with lower limb loss. (Legro 1998). Psychometric analysis supported the reliability and validity of the PEQ for evaluating the function of the prosthesis and the major health related quality of life domains. The PEQ is estimated to take 15 minutes or less to complete. b. The 6 Minute Walk Test (6MWT) is a reliable measure of functional capacity, involves a moderate degree of exercise intensity, and is related to a moderate degree to postural control abilities in persons with lower-limb amputations. (Lin S-J, Bose NH, 2007). This 6MWT is estimated to take 20 minutes or less to complete, including the baseline rest period, set-up, and 6 minutes of continuous walking. This test will not be conducted if the participant is not able to functionally ambulate with use of prosthetic device. c. The Amputee Mobility Predictor (AMP) is a 21 item instrument designed to assess determinants of the lower-limb amputee ability to ambulate. The AMP is estimated to take approximately 15 minutes or less to complete. d. Lower Extremity Functional Scale (LEFS) is a self-reported questionnaire containing 20 questions about a person's ability to perform everyday tasks. The LEFS is anticipated to take approximately 10 minutes or less to complete. e. The Disabilities of the Arm, Shoulder, and Hand (DASH) outcome Measure is a 30-item, self-report questionnaire designed to

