
measure physical function and symptoms in people with musculoskeletal disorders of the upper limb. The DASH is estimated to take approximately 10 minutes or less.f. Functional Mobility Assessment (FMA) is a self-report questionnaire to assess perceived user function related to assistive technology use. The FMA is expected to take approximately 10 minutes or less.g. Prosthetic Device Use History: Compliance with prosthesis use affects activities of daily living (ADLs) as well as impacting social interaction. The participant's prosthetic devices (both pre and post procedure) will be evaluated and a history will be obtained from the participant to determine average daily use and related issues/concerns. This questionnaire is estimated to take approximately 30 minutes for the subject to complete.h. Physical Examination: A physical examination will be conducted to evaluate general UE and LE function and specifically the amputation stump. The stump characteristics will be recorded, including measurements, range of motion, strength, skin integrity/areas of pressure, pain and prosthesis/socket interface. This physical examination is anticipated to take approximately 30 minutes to complete. If upon examination, it is determined that the participant is at increased risk for developing pressure ulcers and/or the participant's current wheelchair and seating is not addressing their needs, they will be referred to the UPMC Center for Assistive Technology for a full assistive technology evaluation per routine clinical care.6. CT Scan with 3D renderings or MRI (Visit 4 PO, Visit 5 PO and Visit 6 PO).7. All participants who are women of child bearing potential will receive a urine pregnancy dip test. If the test result is positive the subject will not continue to the CT or MRI scan. (Visit 4 PO, Visit 5 PO and Visit 6 PO)8. Psychosocial assessment (Visit 1 PO, Visit 3 PO, Visit 4 PO, Visit 5 PO and Visit 6 PO)will be conducted satisfaction with surgical outcomes, quality of life and functional outcomes and improvement in self-esteem, psychiatric distress, and psychological coping.9. Structured Clinical Interview for DSM-IV (SCID) (Visit 4, 5, and 6 PO only) to evaluate any change in the presence/absence of psychiatric disorders and will be compared to PGSV1 SCID results. This SCID will take approximately 45-60 minutes of the subject's time to complete.10. 2D Photographs will be collected at each of the post op visits 11. Limb Pain Assessment will be collected at each of the post op visits . 12. Core Needle Biopsy of fat grafting site - POV3 and POV5 only -(this will only be done with subjects where it is determined by the PI that the biopsy will not interfere with the desired outcome of the fat grafting). In subjects where the biopsy is considered to be appropriate, core biopsies will be taken from the area treated with standard fat graft or treated with SVF concentrated fat graft. These samples will be histologically analyzed for differences in vascularity and other evidence of in vivo activity. The samples will be processed within the UPMC system. The research coordinator will provide telephone follow up 48 to 72 hours to the subject post biopsy. This contact is to obtain a subject self report assessment of signs and symptoms of an adverse event post biopsy (i.e., excessive bleeding, redness, extreme tenderness, and potential signs of infection) as a post procedure standard of care safety assessment. Procedures for Study post operative visits #1-12 usually occur on the same day; however, due to coordination of participant's schedules and travel distance the procedures may be performed on different days as long as the completion of the procedures do not exceed a length of 4 days total. In

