2.15.3 Will biological specimens be stored without identifiers or linkage codes? *

[reviewer notes-]

Section 2 - Research Design and Methods

2.16 Will research participants be asked to provide information about their family members or acquaintances?

* No

2.16.1 Describe what information about the third party will be obtained from the participant:

2.16.2 If the information about the third party is of a private nature, can the identity of the third party be readily ascertained or associated with this information?

*

Describe the private information that will be collected and recorded about the third party:

[reviewer notes-]

Section 2 - Research Design and Methods

Section: Section 2 - Research Design and Methods

2.17

What are the main outcome variables that will be evaluated in this study?

Primary outcomes: Improvement of pain at the amputation site, improved ability to tolerate a prosthesis, and generation of a stable volume of adipose tissue at the amputation site (as measured by clinical assessment by rehabilitation sciences and prosthetics team, quality of life measures, and high resolution imaging). This will be compared between the standard fat grafting group (n=15) and the adipose cell enriched fat grafting group (n=15). Secondary outcomes: Local and systemic complications resulting from fat graft procedure (infection, fat necrosis, hematoma, seroma); basic assays of adipose cell behavior to elucidate the functional properties of adipose cells used for grafting, with correlation to outcomes.

2.18

Describe the statistical approaches that will be used to analyze the study data.

* Addressed below:

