Pain and Serial computed tomography imaging will be performed and measured as parametric data sets before fat grafting and afterwards at various time points using a paired t-test model. Repeated measures analysis of variance will be used to evaluate change over time in all outcome measures. Using standard conventions of alpha=0.05 and beta=0.8, an enrollment of thirty patients may provide sufficient power to detect a Cohen's effect size of about 0.9 which is anticipated to be adequate for detecting clinically meaningful differences in the volume of soft tissue. A composite functional score will be constructed from the prosthetics and occupational therapy evaluations and compared between study groups. The details of this analysis, including which evaluations will be included in the score and relative weight, can be best determined as the study progresses and initial data sets are acquired. Additionally, each assessment score from the specific tests will also be considered individually for comparison.

[reviewer notes-]

Section 2 - Research Design and Methods

2.19

Will this research be conducted in (a) a foreign country and/or (b) at a site (e.g., Navajo Nation) where the cultural background of the subject population differs substantially from that of Pittsburgh and its surrounding communities?* No

Note that copies of training records, licenses, certificates should be maintained in the study regulatory binder and are subject to audit by the Research Conduct and Compliance Office (RCCO).

Section: Section 2 - Research Design and Methods

In addition, individuals planning to conduct human subject research outside the United States must complete an optional module on the CITI training website: International Studies. Click [here](#) to access the instruction sheet for accessing optional CITI modules.

- 2.19.1 Address the following for each of the foreign/culturally different sites where this research will be conducted:
- Name of site
 - Name of authorized individual (e.g., IRB Chair) from the local IRB or other human subject protections entity that is responsible for the review and approval of the project; upload approval letter with an English translation, if applicable
 - Name and qualifications of the site collaborator responsible for the conduct of the research (e.g., site PI)
 - The anticipated number of subjects that will be enrolled at that site
 - If Federally funded, provide the Federalwide Assurance number (FWA) assigned to the site *

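### The trial is labelled non-blinded throughout, and nothing masks the unnamed person who measures CT/MRI graft volume, a primary outcome whose described measurement does not need the arm

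*Combined protocol and SAP*

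**What the plan says.** Section 2.3 gives one unqualified label: "Prospective, Randomized, Non-blinded, Surgical outcomes, Pilot study assessing clinical outcomes following fat grafting for pain at amputation sites". No role is excepted there, and no masking procedure appears elsewhere in the text.

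Section 2.17 lists three primary outcomes: pain at the site, ability to tolerate a prosthesis, and a stable volume of adipose tissue. They are described "as measured by clinical assessment by rehabilitation sciences and prosthetics team, quality of life measures, and high resolution imaging" and are to be compared between the two groups of 15. The study-design paragraph of the abstract (CS2.1) also lists graft retention as a primary measurement.

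On imaging, section 2.6 says "Volume measurements of the implanted material will be made on all post-procedural CTs or MRIs". Radiology reviews the images, but the person who makes the volume measurement is not identified. Section 2.7 places the post-operative scans at months 6, 12 and 24.

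On function, 2.7 has the prosthetist and therapist carry out the assessments at the same three visits and "select the appropriate assessments based on the participant's functional status, amputation site(s), and assistive technology used". The set includes the 6-minute walk, the Amputee Mobility Predictor (AMP) and a stump examination: "The stump characteristics will be recorded, including measurements, range of motion, strength, skin integrity/areas of pressure, pain and prosthesis/socket interface". Section 2.18 adds: "A composite functional score will be constructed from the prosthetics and occupational therapy evaluations and compared between study groups".

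Two further staff readings are described in 2.7. The PI or a co-investigator grades limb volume and appearance at each of post-operative visits 1 to 6. Core biopsies are taken in selected subjects: "These samples will be histologically analyzed for differences in vascularity and other evidence of in vivo activity". Neither reading is masked, and 2.17 names neither as a primary measure.

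**The concern.** The hypothesis is directional: section 1.1 expects enrichment to improve graft retention and outcome. Someone who knows the arm and marks the boundary of the grafted tissue on a scan can, without intending to, draw it more generously in one arm. The same holds, less directly, for encouragement during a walk test or the scoring of a mobility item. Randomization does not remove this kind of difference and a larger sample does not dilute it.

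Graft volume is where the gap matters most. It is a primary outcome, it is measured by staff, and 2.18 justifies the sample size by the ability to detect differences in soft-tissue volume. It is also the easiest outcome to protect, because scans can be stored and read later by code. If the trial reports better retention with enrichment, the first question will be whether the reader knew the arm. As written, the plan gives no answer.

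**Working it through.** **1. Who needs the arm?**

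| Task | Done by | Arm needed for the task as described? |
|---|---|---|
| Cell isolation, mixing, injection (2.6) | Surgeons, cell laboratory | Yes |
| CT/MRI volume measurement (2.6) | Not named; radiology reviews images | Nothing described needs it |
| Biopsy histology (2.7) | Not named; processed within UPMC | Nothing described needs it |
| Walk test, AMP, stump examination (2.5.1, 2.7) | Prosthetist and/or therapist | No; tests are chosen by function, site and technology |
| Volume/appearance grading (2.7) | PI or co-investigator | No, but the rater may be the operating surgeon |
| Pain form, PEQ, LEFS, DASH, FMA, SF-36 | Participant | Masking staff does not apply |

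For imaging, the conclusion rests partly on silence, because the plan describes neither the reader nor the method of separating graft from native tissue. That silence is itself a reason to name the role.

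**2. The plan's own design figure.** Section 2.18 gives alpha 0.05, 80% power (printed as beta = 0.8), 30 patients and a detectable effect of about 0.9 SD. With 15 per arm and the normal approximation, detectable d = (z_alpha + z_power) × √(2/15).
- One-sided: (1.645 + 0.842) × 0.365 = 0.91, which matches the plan.
- Two-sided: (1.960 + 0.842) × 0.365 = 1.02, which does not.

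The plan does not state sidedness. That is a separate matter, and masking changes neither figure.

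**3. Illustration of assessor bias.** The size of the bias is an assumption with no source in the documents. Suppose there is no true effect and unmasked assessment shifts one arm by d SD. The rejection rate of a two-sided 5% two-sample t-test is P(|T| > t_crit), where T is noncentral t with 2n − 2 degrees of freedom and noncentrality d × √(n/2). For n = 15, t_crit = 2.048 on 28 df and √(15/2) = 2.739.

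| Assumed d | Noncentrality | Rejection rate |
|---|---|---|
| 0 | 0 | 5.0% |
| 0.1 | 0.27 | 5.8% |
| 0.2 | 0.55 | 8.3% |
| 0.3 | 0.82 | 12.5% |
| 0.5 | 1.37 | 26.2% |

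The AMP is "designed to assess determinants of the lower-limb amputee ability to ambulate", so fewer subjects would contribute to it. If four or three of the five randomization blocks of six (3.12) were lower limb, giving 12 or 9 per arm, d = 0.2 to 0.5 gives about 8 to 22% or 7 to 17%. The number of lower-limb blocks is also assumed. The t-test is a simplification, since 2.18 names a paired t-test and repeated-measures ANOVA.

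**4. Why the table should not be read across to imaging.** Section 2.6 expects volumes to be within 5% of the true value. As a rough check, assume volumes spread evenly over the 5 to 300 cc defect range in 3.13.
- Mean = (5 + 300)/2 = 152.5 cc.
- SD = 295/√12 = 85 cc.
- A full 5% error at the mean, all in one arm's favour = 0.05 × 152.5 = 7.6 cc.
- 7.6/85 = 0.09 SD, which lies below the 0.1 SD row, so the error rate stays under 6%.

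On a percent-retention scale the shift could be larger relative to the SD, and the 5% is an expectation rather than a validation result.

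**The case against.** **It is a disclosed choice in a pilot.** The form asks for a summary of the design, and a one-line answer is reasonable. The IDE protocol (CS10.1) and the study schema (2.6) are attachments that cannot be seen here and may say more. This limits the claim to the text available. It does not remove the point, because this text compares arms on a primary outcome at alpha 0.05 and gives no reason for leaving the reader unmasked.

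**Imaging is objective.** The 5% expectation suggests that any reader effect on volume may be small. That stands, and it is why no inflation figure is attached to imaging. It does not settle the matter while the reader and the method are undescribed.

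**The functional tests are not firmly primary.** Section 2.17 refers to clinical assessment by the team without naming the walk test or AMP. The composite in 2.18 has no fixed components, and several candidates are self-report. Section 3.12 calls pain and ability to wear a prosthesis the major endpoint. This stands, so therapist masking is secondary.

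**Therapist masking would be partial.** Therapists judge weight-bearing readiness jointly with the PI (2.7), the study team meets monthly (5.13), the fat-grafting record enters the UPMC chart (2.14), and patients may know their arm. This stands too.

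A reader might also infer three stronger things that the documents do not support:
- That the choice of tests follows the arm. Section 2.7 ties it to function, site and technology.
- That the predecessor protocol was disapproved for lack of blinding. CS1.1.1 lists it among the lesser concerns.
- That masking staff would protect the pain outcome. Pain is recorded by the participant.

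**Conclusion.** The point holds for the imaging outcome. A staff-measured primary outcome is compared between arms, the measurer is unnamed, the task as described does not need the arm, and nothing in the available text masks it. It holds in weaker form for the biopsy reading, which is not primary, and for the therapist-administered tests, whose place in the primary outcome is not fixed and whose masking can only be partial.

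The size of any bias cannot be derived from the documents. The 5.8%, 8.3% and 26% figures rest on an assumed shift, a two-sided t-test at a single visit and 15 per arm. It would be tempting to report them as the inflation to expect in this trial or in its volume comparison; neither is supported. The recommendation does not depend on them. It rests on the bias being cheap to prevent and on a volume result being hard to defend without masked reading. The change should be made, but its absence does not invalidate the trial.

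**What to change.** **In 2.3 and 2.6.** Name the role that measures graft volume. State that this person is neither an operating surgeon nor a member of the cell-laboratory staff, and measures every scan, including any already stored, by study code without arm, operative or laboratory records. Read biopsy slides the same way. State that operating surgeons and cell-laboratory staff are unmasked. Do not declare investigators as a class unmasked, because the reader or an assessor may be a listed co-investigator.

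**In 2.7, secondary and where feasible.** The existing prosthetics and therapy assessors are not told the arm at post-operative visits 4 to 6, and patients are asked not to disclose it. Any unmasking, and any assessment made before the change, is flagged in the data.

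**In 2.18.** State that the PI or co-investigator appearance and volume grading is unmasked and supportive only. State also that, if patients know their arm, between-arm differences in self-reported pain, prosthesis tolerance and quality of life cannot be separated from expectation.

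**Cost.** Protocol wording, coded image and slide sets, and assessor files without operative or laboratory records. Section 5.1.1 already assigns study ID codes, so the addition is withholding the arm. No visit, procedure or sample-size change follows. The main downside is that therapist masking will be incomplete. If follow-up has already begun (the supporting documents list a 2018 enrollment-hold communication), masked and unmasked functional data will be mixed. Stored scans can still be measured masked.
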